# 10.5 Sample Size

Group sample sizes of 25 in Nivolumab combination group and 25 in Nivolumab-only monotherapy group achieve 80% power to detect a difference between the group ORRs of 34%. The ORR in Nivo-only group is assumed to be 15%. The ORR in Nivolumab combination group is assumed to be 49% under the alternative hypothesis. The test statistic used is the two-sided Z-Test with unpooled variance. The significance level of the test is 0.05.

The powered sample size and expected ORR is based upon results from the phase II study of nivolumab in HCC as well as other checkpoint inhibitors (e.g. pembrolizumab) in HCC. If the results do not show significant efficacy, the HRs and 95% CIs will be estimated to quantify the magnitude of the efficacy in each treatment arm. If results are sufficiently promising, then the protocol may be amended to expand the cohort to allow comparison between treatments with higher confidence.

### 10.6 Randomization

The randomization list will be generated by the biostatistics department according to the proposed sample size and study design and uploaded into the REDCap randomization module. All centers will receive randomization assignment from NYU as the coordinating center. If a patient is randomized, but not ultimately treated, then the coordinating center (NYU PCC) must be notified. Randomization will be stratified within center.

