# **Protocol Summary**

[figure not shown]
i rotocor carrilla	,	
Title	A Phase II, Randomized, Controlled Trial of Nivolumab in Combination with BMS-986253 in Advanced Hepatocellular Carcinoma (HCC) Patients	
Short Title	Nivolumab Combined with BMS-986253 in HCC Patients	
Brief Summary	A phase II clinical trial is utilized to examine whether BMS-986253 (25 subjects) when combined with Nivolumab offers improved radiographic objective response rates (ORR) over Nivolumab monotherapy (25 subjects in advanced HCC patients. Primary endpoint, ORRs, will be assessed at 2 month increments while on treatment. Safety will be verified for the Nivolumab/BMS-986253 combination. Secondary endpoints of time to response (TTR), duration of response (DOR), progression free survival (PFS), and overall survival (OS) will also be assessed. Pre- and on-treatment tumor biopsies will be utilized for translational/correlative research.	
Phase	Phase 2	
Objectives	
 
Determine the ORR of BMS-986253 in combination with Nivolumab.
 
Determine the safety of BMS-986253 in combination with Nivolumab.
 
Determine the TTR, DOR, PFS, and OS for subjects receiving BMS-986253 in combination with Nivo.
 
Exploratory study of the tumor microenvironment (TME) using novel NYU technologies of 30-parameter flow cytometry and single cell RNAseq on pre- and on-treatment fresh core biopsies.
 
	
Methodology	Randomized, controlled, single blind trial	
Endpoint	Primary Endpoints: ORR of BMS-986253 in combination with Nivolumab in comparison to Nivolumab monotherapy and safety of BMS-986253 in combination with Nivolumab.  Secondary Endpoints: TTR, DOR, PFS, OS, and exploratory analysis of the HCC TME in subjects receiving either BMS-986253 in combination with Nivolumab in comparison to Nivolumab monotherapy	
Study Duration	The duration of this study from enrollment until completion of data analysis is up to 6 years	
Participant Duration	2-5 years	
Enrollment Period	2 years	
Duration of IP administration	2-5 years	
Population	50 total male and female participants: 25 participants Nivolumab monotherapy group, 25 participants Nivolumab/BMS-986253 combination, Age ≥ 18, Two U.S. sites	
Study Centers/Sites	Multicenter (Two): NYU Langone Health and Univ. of Pennsylvania	
Number of participants	50 participants across 2 sites	
Description of Study Agent/Procedure	Nivolumab 240 mg IV every 2 weeks + BMS-986253 2400 mg IV every 2 weeks	

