Reference Therapy	Nivolumab 240 mg IV every 2 weeks	
Key Procedures	Key procedures include pre- and on-treatment biopsies, peripheral blood for IL-8 determination	

Study number: S18-01028 Version: 11.0 Page 2

With the recent results of the CheckMate-040 study in HCC patients, we		
Statistical Analysis  34% would be able to be detected at 80% power. Thus an absolute ORR the combination group of 49% would be able to be detected at 80% power assuming the 15% ORR for the Nivolumab monotherapy group, utilizing the two-sided Z-Test with unpooled variance and significance level of 0.05.	Statistical Analysis	would expect a primary endpoint, ORR of 15%, for the Nivolumab monotherapy group (n=25 participants). For the combination group (Nivolumab + BMS-986253) with n=25 participants each, a change in ORR of 34% would be able to be detected at 80% power. Thus an absolute ORR for the combination group of 49% would be able to be detected at 80% power, assuming the 15% ORR for the Nivolumab monotherapy group, utilizing the two-sided Z-Test with unpooled variance and significance level of 0.05. Secondary endpoint outcomes (TTR, DOR, PFS, OS) will be analyzed using the Kaplan-Meier method. Exploratory endpoints for translational and

Version: 11.0

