#### 5.8 Total Number of Participants and Sites

Recruitment will end when approximately 50 participants are randomized over 2 years. It is expected that approximately 70 participants will be screened in order to enroll and produce 50 randomized participants. There will be no international sites. Other U.S. sites may be considered to facilitate enrollment.

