#### 10.4.2 Analysis of the Primary Efficacy Endpoint(s)

ORR will be defined as the best objective response using RECIST v.1.1 criteria based on MRI or CT scan evaluations following treatment. ORR will be compared by two-sample proportion test between BMS-986253 in combination with Nivolumab in comparison to Nivolumab monotherapy. P-values will be two-sided and any p-values less than 0.05 will be significant. No adjustment to significance determination for multiple comparisons will be made.

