#### 10.4.3 Analysis of the Secondary Endpoint(s)

Secondary Endpoints, including TTR, DOR, PFS, OS, and exploratory analysis of the HCC TME, will be performed. TTR and DOR will be described and PFS and OS will be compared between subjects receiving BMS-986253 in combination with Nivolumab in comparison to Nivolumab monotherapy. Kaplan-Meier method will be used to analyze the median TTR, DOR, PFS, and OS. Categorical variables will be compared by two-sample proportion test, survival outcomes will be compared by log rank test, and continuous outcome will be compared by two-sample t-test.

Version: 11.0

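### Randomisation is stratified by centre, but PFS and OS are compared by a log-rank test with no stratum, which costs power if centre is strongly prognostic

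*Combined protocol and SAP*

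**What the plan says.** Allocation: section 10.6 states "Randomization will be stratified within center". I read this as a separate allocation sequence for each centre. No other stratification factor is named. The Protocol Summary plans "50 participants across 2 sites", and section 5.8 adds that "Other U.S. sites may be considered to facilitate enrollment".

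PFS and OS: section 10.4.3 states that "survival outcomes will be compared by log rank test". No stratum or covariate is mentioned there or under the general approach in 10.4.1.

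Hazard ratios: if efficacy is not significant, section 10.5 says that "the HRs and 95% CIs will be estimated to quantify the magnitude of the efficacy in each treatment arm". It names no model and no strata.

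ORR: section 10.4.2 states that "ORR will be compared by two-sample proportion test". Section 10.5 identifies the test: "The test statistic used is the two-sided Z-Test with unpooled variance". The Protocol Summary agrees ("two-sided Z-Test with unpooled variance and significance level of 0.05").

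Section 10.1 defers a formal SAP to before database lock. The documents contain no separate SAP text.

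**The concern.** Stratified allocation balances the arms within each centre. If centre affects prognosis, that balance makes the treatment comparison more precise, but an analysis that ignores centre does not use the gain. For a log-rank test the result is a true size below 5% and lower power. The unstratified hazard ratio also lies nearer to 1 than the within-centre ratio.

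The plan gives no reason for omitting the only factor used in the randomisation. If the choice stays open, stratified and unstratified results could both be produced and one preferred after the outcomes are known.

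**Working it through.** **The plan's own figure.** Power is stated only for ORR: 15% v 49%, 25 per arm, two-sided 0.05, unpooled Z-test.

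- SE = √[(0.15×0.85 + 0.49×0.51)/25] = √(0.3774/25) = 0.1229
- Power = Φ(0.34/0.1229 − 1.96) = Φ(0.807) = 79.0%. Exact enumeration gives 79.1%.

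The stated 80% is reproduced to within about one point. No power, HR or event number is given for PFS or OS.

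**Log-rank comparison.** With O, E and V the observed events, expected events and variance in one arm:

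- unstratified: Z = (O − E)/√V, with all 50 patients in one risk set
- stratified: Z = Σ(Oc − Ec)/√ΣVc, summed over centres c

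From the documents: 50 patients, 1:1, two centres, two-year enrolment (Protocol Summary). Assumed, because the documents do not give them:

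- exponential times, uniform accrual over 24 months plus 12 months of follow-up
- centres of 30/20 or 40/10 patients, balanced exactly or by permuted blocks of 4
- control median 4, 9 or 16.7 months (section 2.2.2 gives OS medians of 8.9 and 16.7 months by best response in the earlier nivolumab study; 4 is assumed)
- treatment HR 0.5, and a centre HR in either direction

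There were 100,000 simulated trials per size and 60,000 per power. At treatment HR 0.5 there were 25 to 46 events.

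| Centre HR | Stratified minus unstratified power, all settings (points) | Median 9, 30/20, exact balance: unstratified v stratified |
|---|---|---|
| 1 | −2.0 to −0.6 | 52.9% v 51.5% |
| 1.5 | −0.5 to +0.4 | – |
| 2 | +1.0 to +4.6 | 48.1% v 51.1% |
| 3 | +2.8 to +13.3 | 40.4% v 50.1% |

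Permuted blocks of 4 change little: 52.9 v 51.5%, 48.0 v 51.1% and 40.8 v 50.2% at centre HR 1, 2 and 3. Power stays below 64% in every setting.

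**Size with no treatment effect.** At centre HR 1: 5.2–5.8% unstratified, 5.1–5.6% stratified. At centre HR 3: 3.2–4.6% v 5.1–5.6%. Ignoring centre lowers the size.

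**Different assumptions.** A second simulation used medians of 6 and 15 months, uniform censoring over 12 to 36 months, centre splits of 50:50 and 76:24, and 20,000 trials per setting. At treatment HR 0.5, median 6 and a 50:50 split, unstratified v stratified power was 58.8 v 57.4% (centre HR 1), 57.1 v 57.2% (1.5), 53.4 v 57.5% (2) and 44.1 v 56.5% (3). The pattern is the same.

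**Hazard ratio.** With a within-centre HR of 0.50 and centre HR 3, the median estimate is 0.51–0.56 unstratified and 0.50 stratified.

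**ORR.** Exact enumeration, 25 per arm, centre splits of 15+10 and 20+5 in each arm:

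| Centre odds ratio | Unpooled Z power | Centre-stratified CMH power | Unpooled Z size, 15% null |
|---|---|---|---|
| 1 | 79.1% | 75.7–75.9% | 5.53% |
| 2 | 79.2–79.3% | 76.4–76.6% | 5.34–5.44% |
| 4 | 79.6–80.0% | 77.6–78.8% | 4.82–5.30% |
| 8 | 80.0–81.0% | 78.7–82.9% | 3.87–5.18% |

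At centre odds ratios 1 to 4, coverage of the 95% CI for the ORR difference is 93.4–94.6% unstratified and 93.4–93.8% with a Mantel-Haenszel difference. Stratifying brings no gain.

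**The case against.** The strongest reply is that the harm depends on a centre effect for which the documents offer no evidence. Two U.S. sites enrol under common criteria (section 5.1: Child-Pugh up to 7, ECOG 0–1, no prior systemic therapy). If centre matters little, stratifying does nothing or costs up to 2 points. This stands, and it is why the loss can only be stated conditionally.

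PFS and OS are also secondary, with no power claim. The shift in the HR is small beside its uncertainty: SE(log HR) ≈ 2/√D, or 0.29 to 0.40 for 46 to 25 events, so a 95% CI around 0.5 runs from 0.28–0.89 to 0.23–1.10. The shift is also the expected gap between a marginal and a within-centre ratio, not a mistake in the plan. This too stands and keeps the point minor.

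The SAP of section 10.1 could add the stratum. That offers a place for the repair, but the protocol already names the test without one.

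A reader might infer that the primary ORR test suffers in the same way. The figures do not support this: the unpooled Z-test has more power than CMH up to a centre odds ratio of about 4, and CMH leads only at 8, in three of four settings. Nor is the ORR test always conservative under a strong centre effect, since its size still reaches 5.30% at odds ratio 4 and 5.18% at 8. A reader might also think the ORR test undefined because 10.4.2 is general, but section 10.5 and the Protocol Summary both name it.

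**Conclusion.** The mismatch is real for PFS, OS and the hazard ratios. It is minor. It does not inflate the false-positive rate.

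Under the assumed settings, the unstratified log-rank test gives up about 1 to 5 points of power at a centre HR of 2 and about 3 to 13 at 3, where its size falls to about 3–5%. Break-even is near a centre HR of 1.5. The trade is uneven: a cost of at most about 2 points if centre is irrelevant, against a larger gain if it is strongly prognostic.

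The centre effect, the split between centres, the block scheme and the medians are all assumptions. The direction of the result is secure, but its size in this trial is unknown. Nothing here calls the primary ORR analysis into question.

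**What to change.** In section 10.4.3, or in the SAP that section 10.1 places before database lock:

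- compare PFS and OS by a log-rank test stratified by centre
- estimate the hazard ratios of section 10.5 from a Cox model stratified by centre
- if sites are added under section 5.8, pool very small ones into one stratum by a rule based on site size alone, because a site with patients from only one arm adds nothing to a stratified test

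Keep the unpooled Z-test of section 10.5 as the primary ORR test, with no change to the ORR analysis.

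Centre is already known for every patient, so no new data are needed. Editing 10.4.3 is a protocol amendment and needs IRB approval under section 13.2; the SAP route is an alternative. The documents do not say whether the SAP has been written. Section 7.2.4 reports specimen analysis complete as of February 2024, so outcome data may be well advanced, and the choice should be fixed and dated without sight of outcomes by arm. The statistical cost, if centre has no effect, is 0.6 to 2.0 points of log-rank power in the main simulations.

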## 11 Source Documents and Access to Source Data/Documents

Source data is all information, original records of clinical findings, observations, or other activities in a clinical trial necessary for the reconstruction and evaluation of the trial. Source data are contained in source documents. Examples of these original documents, and data records include: hospital records, clinical and office charts, laboratory notes, memoranda, subjects' diaries or evaluation checklists, pharmacy dispensing records, recorded data from automated instruments, copies or transcriptions certified after verification as being accurate and complete, microfiches, photographic negatives, microfilm or magnetic media, x-rays, subject files, and records kept at the pharmacy, at the laboratories, and at medico-technical departments involved in the clinical trial. It is acceptable to use CRFs as source documents. If this is the case, it should be stated in this section what data will be collected on CRFs and what data will be collected from other sources.

Trialmaster, an electronic database capture system will be created to record the data for this trial. Research coordinators will input clinical trial data into the database. This database is password protected and only the PI, assigned study team members, and CTO staff will have access to the database. DataCore, a core resource of the institution, will provide the primary data collection instrument for the study. All data

Version: 11.0

requested in the system must be reported. All missing data must be explained. The quality assurance specialists will monitor this trial every 4-6 weeks for data entry accuracy.

Source documentation should be consistent with data entered into any electronic medical record or Trial master. Relevant source documentation to be reviewed by the assigned QA specialist throughout the study includes:

- 1. Baseline measures to assess pre-protocol disease status
- 2. Concurrent medications
- 3. Treatment records
- 4. Adverse events

# 12 Quality Assurance and Quality Control

This study will be monitored according to the monitoring plan detailed below. Sub-site monitoring will follow parameters detailed in Section 12.1. The Investigator will also ensure that the monitor or other compliance or quality assurance reviewer is given access to all the above noted study-related documents. If an on-site monitoring visit is necessary, the Investigator will provide access to all study related facilities (e.g. pharmacy, diagnostic laboratory, etc.), and ensure there is adequate space to conduct the monitoring visit. A risk-based, data-driven monitoring approach will be used to verify data for this trial which will also include a centralized review of data for quality, trends, consistency and general safety review. At each visit, the monitor will review various aspects of the trial including, but not limited to: screening and enrollment logs; compliance with the protocol and study manual and with the principles of Good Clinical Practice; completion of case report forms; source data verification; study drug accountability and storage; facilities and staff.

At any time during the course of the study, representatives of the FDA and/or local regulatory agencies may review the conduct or results of the study at the investigational site. The investigator must promptly inform NYU PCC CTO and BMS of any audit requests by health authorities, and will provide BMS with the results of any such audits and with copies of any regulatory documents related to such audits.

In accordance with HIPAA and associated privacy regulations, a patient's authorization to use personal identifiable health information may be required from each patient before commencement of research—activities. This authorization document must clearly specify what parties will have access to a patient's personal health information, for what purpose and for what duration.

At the NYU Perlmutter Cancer Center, all investigator-initiated protocols are subject to a standardized data and safety monitoring, which includes scientific peer review, IRB review and DSMC review as well as internal auditing.

The review of AEs and trial conduct for this trial occurs at several levels:

- (1) Principal Investigator: Adverse events are evaluated monthly by the principal investigator in conjunction with the research nurses, data manager and research team.
- (2) DSMC, quarterly
- (3) Institutional Review Board (IRB): An annual report to the IRB is submitted by the trial PI for continuation of the protocol. It includes a summary of all AEs, total enrollment with demographics, protocol violations, and current status of subjects as well as available research data.

Version: 11.0

In addition, the quality assurance unit will monitor this trial every 4-6 weeks; this includes realreview of all eCRFs to ensure completeness and to verify adherence to the protocol; the completeness, accuracy and consistency of the data; and adherence to ICH Good Clinical Practice guidelines. Additionally, a first subject audit is to be conducted within four weeks of enrollment.

# 12.1 Monitoring of Other Participating Institutions

Monitoring visits are done remotely unless otherwise specified, via remote EMR access. If not possible, secure email exchange will be utilized. The quality assurance specialist will confirm an upcoming monitoring visit with a Site Investigator and staff. If remote EMR access is not available, then the Site Coordinator will ensure that all source documents for subjects are de-identified and labeled only with the subject ID number(s), before emailing all requested documents to the quality assurance specialist within 5 business days from the date of the visit. Any outstanding documents will be listed in the report as a high-priority request for the next monitoring visit. It is expected that response to data clarification requests and other trial-related inquiries will occur throughout the course of the study through regular communication with the site monitor, the Supporter or representatives, and review/entry of data into the electronic study database. Continued non-compliance and failure to submit documentation will result in the suspension of subject enrollment at the site, until the documents have been received.

# 13 Ethics/Protection of Human Subjects

#### 13.1 Ethical Standard

The investigator will ensure that this study is conducted in full conformity with Regulations for the Protection of Human Subjects of Research codified in 45 CFR Part 46, 21 CFR Part 50, 21 CFR Part 56, and/or the ICH E6.

#### 13.2 Institutional Review Board

The protocol, informed consent form(s), recruitment materials, and all participant materials will be submitted to the IRB for review and approval. Approval of both the protocol and the consent form must be obtained before any participant is enrolled. Any amendment to the protocol will require review and approval by the IRB before the changes are implemented to the study. All changes to the consent form will be IRB approved; a determination will be made regarding whether previously consented participants need to be re-consented.

#### 13.3 Informed Consent Process

## 13.3.1 Consent/Assent and Other Informational Documents Provided to Participants

Consent forms describing in detail the study agent, study procedures, and risks are given to the participant and written documentation of informed consent is required prior to starting intervention/administering study product. The following consent materials are submitted with this protocol: Informed Consent.

#### 13.3.2 Consent Procedures and Documentation

Version: 11.0

Informed consent is a process that is initiated prior to the individual's agreeing to participate in the study and continues throughout the individual's study participation. Extensive discussion of risks and possible benefits of participation will be provided to the participants and their families. Consent forms will be IRB-approved and the participant will be asked to read and review the document. The investigator will explain the research study to the participant and answer any questions that may arise. All participants will receive a verbal explanation in terms suited to their comprehension of the purposes, procedures, and potential risks of the study and of their rights as research participants. Participants will have the opportunity to carefully review the written consent form and ask questions prior to signing. The participants should have the opportunity to discuss the study with their surrogates or think about it prior to agreeing to participate. The participant will sign the informed consent document prior to any procedures being done specifically for the study. The participants may withdraw consent at any time throughout the course of the trial. A copy of the signed informed consent document will be given to the participants for their records. The rights and welfare of the participants will be protected by emphasizing to them that the quality of their medical care will not be adversely affected if they decline to participate in this study.

A copy of the signed informed consent document will be stored in the subject's research record. The consent process, including the name of the individual obtaining consent, will be thoroughly documented in the subject's research record. Any alteration to the standard consent process (e.g. use of a translator, consent from a legally authorized representative, consent document presented orally, etc.) and the justification for such alteration will likewise be documented.

The informed consent process and documentation will follow established institutional guidelines.

